8.2.1.2. Moderation of Risk

All of the medications to be used in this study have been evaluated and approved by the FDA for clinical use. The risks and benefits of the specific study medications, of specific study procedures, and of the study as a whole will be explained to participants. After a thorough history, subjects will undergo careful physical, psychiatric, and laboratory examinations to assure the clinical appropriateness and safety of their participation. Close clinical monitoring will ensure the appropriateness and safety of their continued participation including monthly laboratory tests assessing renal and hepatic function. Given the increased risk of lactic acidosis in the setting of alcohol abuse and metformin, daily alcohol intake will be recorded for the purpose of helping to identify any subject who begins to meet criteria for alcohol abuse or dependence following study randomization. Given the increased theoretical risk of serotonin syndrome with lorcaserin, some pro-serotonergic agents have been added to the exclusion criteria, including all monoamine oxidase inhibitor (MAOI) class of antidepressants. Adjunctive medications are allowed to relieve specific clinical symptoms or manage study medication adverse events.

8.2.2. Potential Benefits to Participants

Study medication, all screening tests, laboratory tests, and assessments outlined in this protocol will be provided free of charge. The Behavioral Treatments that will be provided to all participants free of charge is expected to benefit subjects by enhancing their knowledge and providing strategies for dietary modification, exercise, and weight loss. All subjects are likely to benefit from

the general medical advice on improved diet and increased physical activity that all subjects will receive during the study. They can also benefit from the medical monitoring that is performed at baseline and throughout the study. If physical conditions are detected during the study, then subjects will be referred to their local primary care providers for further evaluation and treatment. Furthermore, there is a growing database to support that metformin is associated with modest but significant weight loss in overweight patients with schizophrenia. Similarly, there is a good database to support the efficacy of lorcaserin for weight loss, but not yet in people with schizophrenia. If subjects are randomized to the lorcaserin/metformin combination treatment or to lorcaserin monotherapy, then they may benefit from the treatment, in addition to the behavioral intervention that all subjects will receive. For any subjects that experience weight loss during the study, it is uncertain whether they can maintain their weight loss after the end of the study. However, the behavioral modification program that all subjects received during the study may be associated with more enduring beneficial effects for those subjects that continue to implement these in their daily life routine.

8.2.3. Risk/benefit ratio

The risks associated with participation in this study include benign but relatively frequent gastrointestinal-related side-effects (e.g. diarrhea, nausea/vomiting, and flatulence) that occur early in the course of metformin treatment and usually disappear with the first week of continued treatment. A rare but very serious side-effect is lactic acidosis which occurs in about 3 in 100,000 patient years with about 50% mortality rate. While lactic acidosis is very serious, it primarily occurs in diabetic patients with renal insufficiency, in the setting of multiple serious surgical and medical conditions, including congestive heart failure, and in alcohol abuse. The risk of lactic acidosis increases with age and degree of renal dysfunction. Given these known risk factors of lactic acidosis, the risk of developing lactic acidosis in the current study is limited further by excluding any patients that have one or more of these risk factors or laboratory evidence of reduced renal function. The risk of serotonin syndrome may be increased with the use of lorcaserin. Serotonin syndrome is a rare but serious side effect that is characterized by a constellation of signs and symptoms that can include tachycardia, agitation, confusion, hypertension, rigidity, tremor, hyperpyrexia, and hyperreflexia. One probable case and one possible case of serotonin syndrome were identified among 3,400 subjects who received lorcaserin in the FDA registration trials. Targeted side effect monitoring aimed at detecting serotonin syndrome, or less fulminant serotonin excess, will be performed at each study visit. Furthermore, as part of the behavioral intervention, each subject will be contacted via telephone weekly or biweekly and subjects will also be screening for serotonin excess at those points of contact.

Participants could potentially benefit by receiving a medication treatment that, in combination with behavioral modification, is effective in reducing their weight, and could result in reduced morbidity and risk of other medical conditions. It is judged that the benefits which subjects will receive from

closely monitored treatment, in addition to the societal benefits of important treatment data concerning a disorder with substantial morbidity and mortality, reasonably outweigh the risks to participating subjects.

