3.5.1. Dosing of Study Medications

Subjects will be randomized to 3 groups, see Figure 1.

- Lorcaserin and Metformin-
 - Max dose of 10mg BID of Lorcaserin and max dose of 1,000mg BID of Metformin
- Lorcaserin-
 - Max dose of 10mg BID
- Placebo

Subjects will be randomized to receive lorcaserin 10mg qAM in the MET/LOR and LOR arms or PBO^L qAM. If tolerated, the dose will be titrated up to 10 mg BID at week 1 for 4 weeks. Subjects who tolerate the initial 4 weeks of treatment, in the LOR/MET arm will begin MET 500mg BID at week 4, while the LOR arm and placebo arm will begin PBO^M. At week 6, the LOR/MET arm will have the MET dose increased to 1,000 mg qAM and 500 mg qHS, with corresponding increases in the PBO^M in the other two arms. At week 8 (Visit 6), in the LOR/MET arm, MET is increased to 1,000 mg (2 capsules) BID, with corresponding increases in PBO^M in the other two arms. If this is well tolerated, then subjects continue LOR/MET, LOR/PBO^M, or PBO^L/PBO^M to the end of the study at week 52 (EOS/Visit 17).

Design and titration schedule

[figure not shown]

Figure 1. 52 week randomized, controlled study of lorcaserin/metformin combination treatment, lorcaserin monotherapy or placebo for weight loss in overweight people with schizophrenia. **A.** Subjects are randomized into 3 groups. **B.** Timeline and dose titration for lorcaserin/metformin combination (B.1), lorcaserin monotherapy with placebo to match metformin (B.2), and full placebo arm (B.3) with matching placebos for lorcaserin and metformin, respectively. Subjects continue all study drug until Week 52. SCZ=schizophrenia; BMI=body mass index.

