3.6. BEHAVIORAL TREATMENTS

A behavioral treatment aimed at modifying cardiovascular risk factors, including weight, activity level, blood sugar, blood pressure, and lipids will be provided to all study participants (see Appendix 9). This intervention will be provided by a trained clinician in individualized sessions at all study visits after the Baseline Visit. After the first two sessions, interim telephone calls will be made between study visits to each participant to reinforce elements of the program and to answer questions. The intervention will use the principles of “Behavioral Group-Based Treatment for Weight Reduction in Schizophrenia and Other Severe Mental Illnesses” developed by [name], and colleagues at the University of Pittsburgh. Nine individual sessions will each last approximately 30 minutes. A rating of adherence to the behavioral treatment program will be made using the Behavioral Treatment Adherence Record at each session. The topics of each session are as follows:

- Week 1: Self-monitoring: Awareness of Body Weight and What One Eats
- Week 2: Burning Calories by Exercise
- Week 3: Phone reinforcement
- Week 4: Controlling Urges to Overeat and Snack
- Week 5: Phone reinforcement
- Week 6: Burning calories by Using Energy
- Week 7: Phone reinforcement
- Week 8: Decreasing Food Cues to Overeat and Snack
- Week 9: Phone reinforcement
- Week 10: Developing good eating habits
- Week 11: Phone reinforcement
- Week 12: Self-control of overeating
- Week 14: Phone reinforcement
- Week 16: Changing snack habits

Week 18: Phone reinforcement
Week 20: Revisit Self-monitoring: Awareness of Body Weight and What One Eats
Week 22: Phone reinforcement
Week 24: Revisit Burning Calories by Exercise
Week 26: Phone reinforcement
Week 28: Revisit Controlling Urges to Overeat and Snack
Week 30: Phone reinforcement
Week 32: Revisit Burning calories by Using Energy
Week 34: Phone reinforcement
Week 36: Revisit Decreasing Food Cues to Overeat and Snack
Week 38: Phone reinforcement
Week 40: Revisit Developing good eating habits
Week 42: Phone reinforcement
Week 44: Revisit Self-control of overeating
Week 46: Phone reinforcement
Week 48: Revisit Changing Snack habits
Week 50: Phone reinforcement
Week 52: Increasing success

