3.9. DETAILS OF PROCEDURES

3.9.1. Study Materials

Sites will use a stadiometer for measuring height and receive instructions for clinical laboratory specimen collection, study documents (source documents, behavioral treatment manual, drug logs, etc) and study medication. In addition, sites will be provided with accelerometers, digital scales, and behavioral treatment handbooks for enrolled participants.

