3.9.7. Concomitant/Adjunctive Medications

Concomitant and Adjunctive Medications will be documented using the Other Medications Record (OMR) form at Baseline and all study visits.

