Given that lorcaserin is a serotonin receptor agonist, it has a potential risk of causing side effects associated with serotonin excess including the possible risk of serotonin syndrome. Serotonin syndrome is a rare but serious side effect that is characterized by a constellation of signs and symptoms that can include tachycardia, agitation, confusion, hypertension, rigidity, tremor, hyperpyrexia, and hyperreflexia (Boyer et al. 2005). It has been associated with agonism at the 5HT_{2A} receptor (Nisijima et al, 2001; Isbister et al., 2001) and usually resolves quite rapidly following administration of a 5HT_{2A} antagonist such as cyproheptadine. Because lorcaserin is a 5HT_{2C} agonist, it does not normally induce serotonin syndrome. However, one of the 3,400 subjects exposed to lorcaserin in the registration trials developed symptoms consistent with moderate severity serotonin syndrome, and one subject developed mild symptoms judged possibly consistent with serotonin syndrome. Given that lorcaserin has not previously been studied in people with psychosis or depression, the safety of co-administration of other serotonergic agents has not been well established. The current study will take precautions by excluding patients taking pro-serotonergic agents including meperidine, buspirone, dextromethorphan, triptans, tramadol, ritonavir, tryptophan, ginseng, St. John's wort. The current project provides an excellent opportunity to begin to collect data on the tolerability and safety of lorcaserin in clinically stable patients with schizophrenia taking antipsychotics. Subjects will be instructed in the signs and symptoms of serotonin syndrome and instructed to contact the research clinic or to seek emergency medical care. Side-effect monitoring aimed at psychiatric decompensation using the BPRS, C-SSRS and CGI will be administered regularly, especially during the first 3 months of the trial. Targeted side effect monitoring aimed at detecting serotonin

syndrome, or less fulminant serotonin excess, will be performed at each study visit. Furthermore, as part of the behavioral intervention, each subject will be contacted via telephone each week of the study to review the last behavioral lesson, and during these calls, subjects will be screened for evidence of serotonin syndrome.

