Appendix 8.

**Individual Behavioral Treatment
for
Antipsychotic-Induced Weight Gain in Schizophrenia**

Adapted from

**A BEHAVIORAL GROUP-BASED TREATMENT FOR WEIGHT
REDUCTION IN SCHIZOPHRENIA AND OTHER SEVERE
MENTAL ILLNESSES**

*[name].
[name], M.B.B.S., MPH
University of Pittsburgh School of Medicine*

Schedule of Events

Week 1	Self-monitoring: Awareness of Body Weight and What One Eats
Week 2	Burning Calories by Exercise
Week 3	Phone reinforcement
Week 4	Controlling Urges to Overeat and Snack
Week 5	Phone reinforcement
Week 6	Burning Calories by Using Energy
Week 7	Phone reinforcement
Week 8	Decreasing Food Cues to Overeat and Snack
Week 9	Phone reinforcement
Week 10	Developing good eating habits
Week 11	Phone reinforcement
Week 12	Self-control of overeating
Week 13	Phone reinforcement
Week 14	Changing snack habits
Week 15	Phone reinforcement

Introduction

This is a behavioral intervention designed to help people with schizophrenia and schizoaffective disorder lose weight and lower their risk for heart disease. There are a total of 8 in-person sessions and 7 phone sessions. In-person sessions should be part of the study visit and should take about a half-hour (approximately 10 minutes weigh-in/homework check, 10 minutes instruction, 10 minutes review). Phone sessions should take 10-15 minutes.

At each session, the clinician starts by checking the participant's homework and weight. If the participant is achieving their goals, give plenty of positive reinforcement. If the participant is not meeting their goals, see if you can think of creative ways to find success or see if you can revise the goal to make it more achievable for the participant. Next, the clinician "teaches" the lesson for the day. The lessons are written as scripts, but the wording can be revised so it feels comfortable for the clinician. Finally, during the review phase, the participant should be able to demonstrate understanding of the lesson as well as the homework that should be done in the coming weeks.

At each session, participants receive a diary in which they record their homework and their progress. Participants receive a new diary for each session and hand in the diary from the previous session.

Week 1

Self Monitoring: Awareness of Body Weight and What One Eats

Begin by orienting participant to program and setting weight loss goals (Appendix A).

Lesson:

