Many people believe that exercising increases one's appetite. This is not true. So you don't have to worry that exercising will make you hungry and make you want to eat more. People often ask how much they need to exercise in order to lose weight. The answer depends on what kind of exercise you do. We have a chart that shows how many calories you burn doing different kinds of exercise (Appendix C). In order to be effective, exercise must be done regularly over a long period of time. We'd like you to schedule two 10-minute exercise periods each day to start. One exercise period should be before breakfast and the second should be before your evening meal.

Each week, you should try to increase your total exercise time by 5 minutes. This week, you'll do two 10-minute exercises each day, for a total of 20 minutes. Next week, you can do one 10-minute period and one 15-minute period, for a total of 25 minutes. If it's more convenient, you can do all of your exercise at one time during the day. It's a great idea to plan to exercise with a friend – that way you'll both be more likely to do it.

Homework

Remember, your homework for next week is to:

1. Write down what you eat before all meals and snacks.
2. Record weight and pedometer daily
3. Choose 3 different exercises and do them twice each day!

Week 3

Phone reinforcement

Talk with patient by phone to assess progress. Trouble-shoot if there are problems, otherwise encourage continued success.

Week 4

Controlling Urges to Overeat and Snack

Lesson:

Many overweight individuals have frequent urges to overeat. Unfortunately, they often give-in to these urges, which results in more calories being consumed and more weight being gained. These eating urges may come at any time throughout the day. The urges to eat tend to be stronger at certain times or places. For example, eating urges may appear in mid-morning when breakfast has been missed or when one is shopping at the mall and passes by an ice cream or candy store.

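### Section 8.2.1.1 promises a telephone serotonin screen every week, but no call schedule in the protocol delivers it, and the Appendix 8 manual stops its calls at week 15 without repeating the screen

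*Combined protocol and SAP*

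**What the plan says.** Four places bear on how often subjects are telephoned.

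- **8.2.1.1 (Lorcaserin Risks):** the behavioural programme is said to include calls on which everyone is to be "contacted via telephone each week of the study to review the last behavioral lesson, and during these calls, subjects will be screened for evidence"; the condition looked for is serotonin syndrome.
- **8.2.3 (Risk/benefit ratio):** "each subject will be contacted via telephone weekly or biweekly and subjects will also be screening for serotonin excess at those points of contact".
- **3.6 (Behavioral Treatments):** after the first two sessions, calls fall between study visits. The list that follows runs to "Week 50: Phone reinforcement". The stated purpose is to reinforce the programme and answer questions; serotonin is not mentioned.
- **Appendix 8 (the intervention text):** "There are a total of 8 in-person sessions and 7 phone sessions". Its instruction for each call is: "Talk with patient by phone to assess progress. Trouble-shoot if there are problems, otherwise encourage continued success".

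Treatment lasts the full year: "Subjects continue all study drug until Week 52" (3.5.1, Figure 1 legend). Sites are given "study documents (source documents, behavioral treatment manual, drug logs, etc) and study medication" (3.9.1). Both 8.2.1.1 and 8.2.3 also require targeted serotonin monitoring at every study visit, separately from the calls.

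**The concern.** The telephone screen is offered as a safeguard just before 8.2.3 concludes that benefit outweighs risk, so its stated frequency should be one that sites can deliver. As written, the weekly frequency cannot be met from any listed schedule, and staff working from the manual would find neither the later calls nor the serotonin question.

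The gap falls where contact is thinnest. From week 16 visits are 4 weeks apart, and calls are the only other planned contact. Medicines are recorded at visits: "Concomitant and Adjunctive Medications will be documented using the Other Medications Record (OMR) form at Baseline and all study visits" (3.9.7). A call is therefore the scheduled chance to learn between visits that a subject has started a prohibited serotonergic drug such as tramadol or dextromethorphan (3.5.4). This has some weight because 8.2.1.1 accepts that co-administration with other serotonergic agents is not well studied, while the exclusion criteria still allow one non-MAOI antidepressant up to its maximum approved dose.

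The same calls carry the behavioural reinforcement, so the amount delivered could differ between sites that work from different calendars.

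**Working it through.** No sample-size or power formula applies. The check is a count of scheduled contacts.

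**Inputs**
- Visits after baseline (Appendices 1 and 2): weeks 1, 2, 4, 6, 8, 10, 12, then 16 to 52 every 4 weeks. 7 + 10 = 17.
- Calls in 3.6: weeks 3, 5, 7, 9, 11, 14, then 18 to 50 every 4 weeks. 6 + 9 = 15.
- Calls in Appendix 8: weeks 3, 5, 7, 9, 11, 13, 15 = 7. In-person sessions: weeks 1, 2, 4, 6, 8, 10, 12, 14 = 8. Both counts reproduce the totals the appendix states.
- I read biweekly as every two weeks.

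**Contact weeks (visit or call)**
- 3.6: no call falls in a visit week, so 17 + 15 = 32 of 52. The gaps are 1 week up to week 12 and 2 weeks from then to week 52. The 52 − 32 = 20 weeks without contact are the odd weeks from 13 to 51.
- Appendix 8 calls plus study visits: 17 + 7 = 24 of 52, or 25 if its week-14 session, which has no matching study visit, is held.
- Call weeks common to 3.6 and Appendix 8: 3, 5, 7, 9, 11 = 5.

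**Weeks 17 to 52** (36 weeks, 9 of them visit weeks)

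| Source | Calls | Longest gap between contacts |
|---|---|---|
| 8.2.1.1, weekly | 36, or 36 − 9 = 27 outside visit weeks | 1 week |
| 8.2.3, weekly or every two weeks | 9 (every two weeks, visits counted) to 36 (weekly, calls alone) | 1 to 2 weeks |
| 3.6 | 9 | 2 weeks |
| Appendix 8 | 0 | 4 weeks |

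**Calls alone over 52 weeks.** A weekly schedule would be 52 calls and an every-two-weeks schedule 26. Section 3.6 gives 15/52 = 29% and 15/26 = 58% of these. Appendix 8 gives 7/52 = 13% and 7/26 = 27%.

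**Related slips.** Section 3.6 sends the reader to Appendix 9, but the appendices end at 8. It also gives the number of individual sessions as nine, while its list has 8 lessons, 8 revisits and a week-52 session: 8 + 8 + 1 = 17. Nine matches the number of distinct topics (8 + 1).

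**The case against.** The strongest reply is that the protocol body already settles most of this. Section 3.6 gives a rule (calls between visits) as well as a list, and visits run to week 52, so 3.6 is the natural governing schedule. With visits counted it satisfies 8.2.3. Appendix 8 is adapted from an outside programme and cannot be followed literally here: it says in-person sessions belong to study visits, yet it places one at week 14, when there is no visit. Sections 8.2.1.1 and 8.2.3 are themselves instructions to screen on the calls; the Appendix 8 text only fails to repeat them. All of this stands. What it does not rescue is the weekly promise in 8.2.1.1, the wording in 8.2.3 that places the contact on the telephone, or an appendix that disagrees with the section it supports.

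Three stronger inferences are tempting, and the documents do not support them.

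- **That serotonin monitoring lapses after week 15, or that some site would make no calls from week 17.** Visit monitoring continues to week 52, and a site making no calls would have to disregard 3.6, 8.2.1.1 and 8.2.3 together.
- **That a serotonergic drug started between visits would necessarily go unseen.** Section 3.5.3 requires any added medicine to be discussed with the PI, subjects are taught the symptoms and told to call or seek emergency care, and unscheduled visits cover tolerability and medication changes.
- **That the treatment comparison is biased.** All arms receive the same calls, randomization is stratified by site, and site is a factor in the primary model (7.2).

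**Conclusion.** The inconsistency is real. The weekly telephone screen in 8.2.1.1 is not delivered by any schedule in the protocol. The best available one, 3.6, gives contact every 2 weeks after week 12 and does so only when visits count. The Appendix 8 calendar and call text were not updated to match.

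The consequence is modest. The quoted lorcaserin trials had one probable and one possible case of serotonin syndrome among 3,400 exposed subjects. If 60 to 73 subjects receive lorcaserin (an assumption: two-thirds of 90 to 110 randomized), that rate implies 2/3,400 × 60 = 0.035 to 2/3,400 × 73 = 0.043 expected cases. This is only a guide, because the rate comes from trials outside schizophrenia. The calls are an added layer on top of visit monitoring, and there is no effect on power or on the comparability of arms. The case for acting is that a stated safety frequency should match what sites are told to do, and the correction is cheap.

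**What to change.** 1. Make the 3.6 list the governing call schedule. Restate 8.2.1.1 and 8.2.3 as contact by visit or call, weekly to week 12 and every 2 weeks to week 52. Acknowledge in the amendment that this lowers the weekly promise in 8.2.1.1.
2. Replace the Appendix 8 calendar and session counts with the 3.6 list: calls at weeks 3, 5, 7, 9, 11, 14 and then 18 to 50 every 4 weeks, with the snack-habits lesson at week 16. In 3.6, correct the pointer to Appendix 9 and the count of nine sessions.
3. Add one line to the Appendix 8 call text: ask about the serotonin symptoms the subject was taught and about any new medicine. Positive answers go to a site clinician, who records them on the existing Adverse Events/Side Effects Form and the OMR. Section 3.9.6 has that form rated by a clinician, and the caller may not be one.

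**Cost.** A text amendment and a revised manual, with no visits or calls beyond those in 3.6. I estimate about a minute per call, so about 15 minutes per subject over 15 calls. The downsides are some non-specific positive answers to follow up and a stated screen that is less frequent than 8.2.1.1 now promises. If the sponsor wants to keep the weekly promise, it would have to schedule contact in the 20 weeks that 3.6 leaves empty.
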